3.2.2 SECONDARY ENDPOINTS

1. Change from baseline OA pain in the target knee as assessed by the weekly average of daily pain NRS at Week 24
2. Change from baseline OA function in the target knee as assessed by Western Ontario and McMaster Universities Osteoarthritis Index (WOMAC) physical function subscore (WOMAC Function) at Weeks 12 and 24
3. Change from baseline OA disease activity as assessed by Patient Global Assessment at Weeks 12 and 24
4. Change from baseline in usage of nonsteroidal anti-inflammatory drugs (NSAIDs) and acetaminophen for target knee OA pain

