7.5 CONCOMITANT MEDICATIONS, TREATMENTS, AND PROCEDURES

Details regarding the name, indication, route of administration, dose, and frequency of all medications taken within 30 days prior to the Screening Visit through Week 28 (EOS)/ET will be recorded in the “Prior and Concomitant Medications” eCRF. “All medications” should include prescription, over-the-counter, supplements, as well as herbal or alternative medications.

Procedures or non-drug therapies that are ongoing, new, or modified at or after the Screening Visits must be recorded on the “Procedures and Non-Drug Therapies” eCRF.

AE assessments should include consideration of any new or modified concomitant therapies administered to the subject.

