3.2.2 Secondary Efficacy Endpoints

1. Change from baseline OA pain in the target knee as assessed by Pain NRS at Weeks 24
2. Change from baseline OA function in the target knee as assessed by Western Ontario and McMaster Universities Osteoarthritis Index (WOMAC) physical function subscore (WOMAC Function) at Weeks 12 and 24
3. Change from baseline OA disease activity as assessed by Patient Global Assessment at Weeks 12 and 24
4. Change from baseline in usage of NSAIDs and acetaminophen for target knee OA pain

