12.3 NSAID/Acetaminophen Usage

An NSAID/acetaminophen usage score (NSAID Score) will be computed as outlined in (Dougados, et al., 2011), adapted to this study design. General calculation for each applicable medication is as follows:

$$\text{NSAID Score} = \frac{[\text{eqNSAID}] \times [\text{Duration of Use}] \times [\text{Usual usage}]}{[\text{Time period in days}]}$$

- **eqNSAID (equivalent NSAID/Acetaminophen value):**

$$100 \times \frac{[\text{Usual total daily dose}]}{[\text{Consensus dose equivalent to 150 mg Diclofenac}]}$$

The following consensus dose equivalent settings will be used:

Reference	Medication ^c	Consensus dose equivalent to 150 mg of diclofenac (in mg)
Dougados et al Table 2 ^a	Diclofenac	150
	Diclofenac sodium	
	Cyanocobalamin;diclofenac sodium;pyridoxine hydrochloride;thiamine mononitrate	
	Naproxen	1000
	Naproxen sodium	
	Diphenhydramine hydrochloride; naproxen sodium	
	Esomeprazole magnesium; naproxen	
	Aceclofenac	200
	Celecoxib	400
	Etodolac	600
	Etoricoxib	90
	Flurbiprofen	200
	Ibuprofen	2400
	Diphenhydramine hydrochloride; ibuprofen	
	ibuprofen ;pseudoephedrine hydrochloride	
	Indometacin	150
	Ketoprofen	200
	Meloxicam	15
Additional Medications ^b	Nimesulide	200
	Phenylbutazone	400
	Piroxicam	20
	Tenoxicam	20
	Acetaminophen	3000
	Paracetamol	
	Butalbital;caffeine; paracetamol	
	Caffeine; paracetamol	
	Chlorphenamine maleate;dextromethorphan hydrobromide; paracetamol	
	Chlorphenamine maleate; paracetamol	
	Chlorphenamine maleate; paracetamol ;pseudoephedrine hydrochloride	
	Codeine phosphate; paracetamol	
	Dextromethorphan hydrobromide;doxylamine succinate;ephedrine sulfate;ethanol; paracetamol	
	Dextromethorphan hydrobromide;doxylamine succinate; paracetamol	
	Dextromethorphan hydrobromide;guaifenesin; paracetamol ;pseudoephedrine hydrochloride	
	Dextromethorphan;phenylephrine	
	Diphenhydramine hydrochloride; paracetamol	
	Diphenhydramine hydrochloride; paracetamol ;phenylephrine hydrochloride	
	Guaifenesin; paracetamol ;phenylephrine hydrochloride	
	Hydrocodone bitartrate; paracetamol	
	Hydrocodone; paracetamol	
	Oxycodone hydrochloride; paracetamol	
	Acetylsalicylic acid ;caffeine; paracetamol	3000
	Acetylsalicylic acid	3000
	Acetylsalicylic acid ;caffeine	
	Ketorolac	40
	Nabumetone	2000
	Sulindac	400

^a This full list is taken directly from (Dougados, et al., 2011) and some medications may not have been used by any subject in this study.

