^b For medications not covered in (Dougados, et al., 2011), the above settings will be used based on decision by the Biosplice Therapeutics, Inc., medical director and some medications may not have been used by any subject in this study.

^c Combination medications (active ingredients are semicolon separated) are analyzed after considering the amount of the active ingredient of interest (in bold)

- **Duration of Use:** This will be equal to the number of days medication was used during each 4-week period of interest: [medication end date - medication start date] + 1 (date imputations, if applicable, are performed as described in section 12.1). If medication is ongoing or end date exceeds the period of interest, the end date will be set to the maximum date of interest. If medication start date is prior to the period of interest, the start date will be set to the minimum date of interest (i.e., the maximum possible duration of use within any given time period of interest is 28 days).
- **Usual usage:**

eCRF Option	Value used in calculation
No NSAID / Acetaminophen usage	0
>0-1 days a week	0.5 / 7
2-3 days a week	2.5 / 7
4-5 days a week	4.5 / 7
6-7 days a week	6.5 / 7

- **Time period in days:** 28 days (or 4-week periods).

The sum of all medications used for each 4-week period (Total NSAID Score) will be calculated and summarized. The time periods of interest are as follows:

Nominal Time Period	Actual Study Days
Baseline	Day -28 to -1
Day 1 to Week 4	Day 1 to 28
Week 5 to Week 8	Day 29 to 56
Week 9 to Week 12	Day 57 to 84
Week 13 to Week 16	Day 85 to 112
Week 17 to Week 20	Day 113 to 140
Week 21 to Week 24	Day 141 to 168
Week 25 to Week 28	Day 169 to 196

NSAID scores are only calculated for oral medications. If a subject did not have any NSAID/acetaminophen usage during a time period, their Total NSAID score will be set to 0 for that time period. If a subject terminated from the study early, the Total NSAID score for the period in which they terminated will be considered missing (i.e., an early termination subject must be in-study for the entire 28-day period of interest to compute an NSAID score).

A statistical description (number of subjects, mean, standard deviation, median, minimum, and maximum) of Total NSAID Score at baseline will be provided along with the change from baseline at each subsequent visit. Components of the Total NSAID Score will be provided in a

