listing. Investigator assessment of NSAID/acetaminophen usage will also be provided in a listing.

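### Secondary endpoint 4 is NSAID/acetaminophen use for target knee OA pain, but the only by-arm summary is of all-cause oral use; knee-attributed use is listed and never summarised or compared.

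*SAP*

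**What the plan says.** **The endpoint.** Protocol 3.2.2 gives secondary endpoint 4 as "Change from baseline in usage of nonsteroidal anti-inflammatory drugs (NSAIDs) and acetaminophen for target knee OA pain". SAP 3.2.2 repeats it with the same restriction.

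**The score.** SAP 12.3 builds a score per drug ("General calculation for each applicable medication is as follows") from daily dose relative to a diclofenac-equivalent dose, days of use, usual days per week, and a 28-day denominator. Then: "The sum of all medications used for each 4-week period (Total NSAID Score) will be calculated and summarized". The stated limit on what enters is "NSAID scores are only calculated for oral medications". That sentence shows the oral restriction and no more; the all-cause reading follows from the sum together with the absence of any indication term. The dose-equivalent table also covers acetylsalicylic acid and cold or cough combinations, for example "Chlorphenamine maleate; paracetamol ;pseudoephedrine hydrochloride".

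**What is done with it.** Change from baseline in the Total NSAID Score gets descriptive statistics, on the Safety Analysis Set as for the rest of SAP Section 12, and by treatment group under the general rule in SAP 7.1. Its other role is as a covariate in Sensitivity 2 (SAP Appendix 3).

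**The knee-specific data.** Protocol 7.1.1 and SAP 7.3.4 have the investigator compare use with Day 1 at each later visit, decide whether any change is clinically relevant and, if so, whether target knee OA pain caused it. Protocol 7.5 also collects indication: "Details regarding the name, indication, route of administration, dose, and frequency of all medications". SAP 12.3 disposes of the judgement in one line: "Investigator assessment of NSAID/acetaminophen usage will also be provided in a listing".

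**The planned model.** Protocol 10.4.3 includes change in usage among the secondary outcomes for MMRM, with confidence intervals and P values. SAP 9.3.1 and Appendix 3 leave it out, and SAP Section 13 does not mention the omission.

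**The concern.** A named secondary endpoint should have at least one planned summary by arm that measures what it names. Here the endpoint asks whether the injection changes how much analgesic subjects take for the treated knee. The score asks how much oral NSAID and acetaminophen they take for any reason. The two can diverge when use for other pains or illnesses starts, stops or replaces knee use during follow-up. The information that would separate them is collected at every post-baseline visit but left in a listing, where arms cannot readily be compared. The added noise could hide a real difference in knee-related use, and the clinical study report may end up presenting an all-cause figure under a knee-specific label.

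**Working it through.** The plan states no figure for this endpoint, so there is none to reproduce. The check compares definitions and then works the SAP 12.3 formula on assumed patterns of use, not trial data.

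**1. Definitions side by side**

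| Element | Stated endpoint (3.2.2, both documents) | Total NSAID Score (SAP 12.3) | Investigator assessment (Protocol 7.1.1, SAP 7.3.4) |
|---|---|---|---|
| Drugs | NSAIDs, acetaminophen | NSAIDs, acetaminophen, aspirin, combinations | NSAIDs, acetaminophen |
| Reason for use | Target knee OA pain | Not used | Target knee OA pain, for clinically relevant changes |
| Summary by arm | Needed | Yes, descriptive | None; listing only |

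The column that matches the endpoint's reason for use has no by-arm summary. The column that has one does not use the reason. The SAP gives NSAID usage its own headings only at 7.3.4 and 12.3, and neither fills the gap.

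**2. Can the all-cause score miss a knee-specific change?**

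Formula: score = 100 × (daily dose ÷ equivalent dose) × days of use × usage fraction ÷ 28. The usage fraction is 0.5/7, 2.5/7, 4.5/7 or 6.5/7.

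Assume a subject takes naproxen 1000 mg (equivalent dose 1000 mg) on 2-3 days a week for the knee at baseline, later stops that, and takes the same amount for another reason.
- Baseline: 100 × 28 × (2.5/7) ÷ 28 = 35.7
- All-cause change: 35.7 − 35.7 = 0.0
- Knee-only change: 0 − 35.7 = −35.7

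This is an extreme case, but it shows that the score can miss the whole of the change the endpoint names.

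**3. How much does a short unrelated course add?**

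Acetaminophen 3000 mg/day (equivalent dose 3000 mg) for 7 days, by usage category:
- >0-1 days a week: 100 × 7 × (0.5/7) ÷ 28 = 1.8
- 2-3 days a week: 100 × 7 × (2.5/7) ÷ 28 = 8.9
- 6-7 days a week: 100 × 7 × (6.5/7) ÷ 28 = 23.2

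For comparison, naproxen 440 mg for the knee on 2-3 days a week over the full 28 days scores 44 × 2.5/7 = 15.7. The unrelated week exceeds that in the 6-7 category but not in the two lowest. The item asks for usual days per week over the previous 4 weeks, and 7 ÷ 4 = 1.75 days a week on average, so the top category cannot be assumed.

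**4. Stable background use**

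Aspirin 325 mg on 6-7 days a week scores 100 × (325/3000) × 6.5/7 = 10.1 in each period. If it does not change, its contribution to change from baseline is 10.1 − 10.1 = 0.

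**The case against.** The best defence is that an all-use measure was intended. Protocol Figure 1 lists the endpoint without the knee qualifier, Protocol 10.4.3 speaks only of change in usage, and Amendment 02 took the knee phrase out of the description of the investigator assessment because any use would be collected and assessed. For Sensitivity 2 an all-use score is the sensible covariate, since any analgesic can affect reported pain. The population also limits unrelated use: the target knee must be the main source of pain, widespread pain is restricted, and a stable analgesic regimen is required before Day 1. Randomisation balances the rest in expectation.

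Much of this stands. It supports keeping the score and rules out a claim of bias. It does not close the gap, because the current endpoint text in both documents keeps the restriction, and the SAP, which is later than the amendment, repeats it. If all-use was meant, the endpoint should say so.

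Some stronger readings are tempting but unsupported:
- **That endpoint 4 is not analysed at all.** An all-cause proxy is summarised, and its components and the investigator's judgement are listed.
- **That the score is contaminated by cardiovascular aspirin.** Stable use cancels in the change.
- **That one week of a cold remedy outweighs a month of knee use.** This holds only under some codings, and SAP 12.3 itself notes that some tabulated drugs may not have been taken by anyone.
- **That a simple filter on indication would solve it.** Protocol 7.5 records indication but does not say that the entry identifies the target knee, and as-needed use of one drug for several pains may not be separable.

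**Conclusion.** The mismatch is real and of moderate importance. Use attributed to the target knee is never summarised or compared between arms, so the plan as written does not answer secondary endpoint 4. The consequence is added noise and a different question answered. The documents give no basis for estimating the dilution; the worked scores show what the formula allows and are not a forecast. The primary analysis and the familywise error rate are unaffected, because the endpoint is not among the six hypotheses in SAP Section 9. The conclusion rests on two inferences. One is that the drugs to be scored are not otherwise limited by indication, since SAP 12.3 states no such limit. The other is that the Total NSAID Score is what will stand for endpoint 4: the SAP never labels it so, but no other by-arm summary of usage is planned.

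**What to change.** 1. For endpoint 4, tabulate by arm and visit the number and percentage of subjects with a clinically relevant change in use that the investigator attributed to target knee OA pain, split by direction if direction is recorded.
2. Where the recorded indication identifies the target knee, add a knee-indicated Total NSAID Score as supportive.
3. Keep the existing score for description and for Sensitivity 2, labelled as all-cause oral use.
4. State in SAP Section 13 how endpoint 4 is analysed, including that the MMRM on usage planned in Protocol 10.4.3 is absent from SAP 9.3.1. If the sponsor prefers the all-cause measure as the endpoint, say so there and align the endpoint wording. Label any change made after unblinding as post hoc.

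The cost is SAP wording and tables from data already collected. The downside is that the attribution is a subjective investigator judgement and the recorded indication may be imprecise for some records, which is why the all-cause score should stay alongside.

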10.4.3 ANALYSIS OF THE SECONDARY ENDPOINT(S)

Change over time in secondary endpoints will be characterized using MMRM in order to estimate change from baseline with treatment group, week, treatment \times week interaction and baseline value as covariates. The model will be evaluated for weekly average of daily pain NRS at Week 24 and WOMAC Function and Patient Global Assessment at Weeks 12 and 24, as well as change in NSAID/acetaminophen usage. Unadjusted 95% confidence intervals and *P* values will be reported. The potential confounding effect of change in NSAID/acetaminophen usage on the treatment effect will be considered for sensitivity analysis.

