7.1.2 Mixed-Effects Model for Repeated Measures

A mixed-effects model for repeated measures (MMRM) will be used to evaluate Pain NRS, WOMAC, and Patient Global Assessment outcome measures. The null hypothesis is that the mean difference in the endpoints between the two treatment groups is zero, versus the alternative hypothesis that this difference is not zero. The hypotheses can be expressed as follows:

$$H_0: (\beta_1 - \beta_0)_t = 0$$

$$H_A: (\beta_1 - \beta_0)_t \neq 0,$$

where β_0 refers to the least squares mean change from baseline in the placebo group and β_1 refers to the least squares mean change from baseline in the active treatment group, evaluated at timepoint t .

For Pain NRS, the model will be estimated assuming a Toeplitz variance-covariance matrix. The Toeplitz structure is a more generalized form of autoregressive-1 (AR1) structure, allowing the data to inform how the correlation between within-subject observations decreases over time instead of implicitly defining a uniform decay structure (Kincaid, 2005).

For WOMAC and Patient Global Assessment, the model will be estimated assuming an unstructured variance-covariance matrix, allowing the data to fully inform the correlation between within-subject observations (Kincaid, 2005).

MMRM presumes that missing data are not caused by something observable within the conduct of the trial (i.e. missing-at-random [MAR]). It is plausible to presume a MAR mechanism as there have been no observed tolerability issues to the administration of study injection during the prior development trials. Additionally, the study injection cannot be removed after it has been administered, eliminating study drug discontinuation as a source of treatment estimate confounding.

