7.1.3 Analysis of Covariance

Analysis of Covariance (ANCOVA) will be used for continuous efficacy outcome measures to test the following hypotheses:

$$H_0: (\beta_1 - \beta_0) = 0$$

$$H_A: (\beta_1 - \beta_0) \neq 0$$

In the statement above, β is the least squares estimate in the change in the continuous efficacy outcome from baseline, where β_0 is the estimate for placebo and β_1 is the estimate for the active treatment group. The models will be adjusted for baseline value of the outcome.

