9.3 Secondary Efficacy Analysis

9.3.1 Main Analysis

Change over time in secondary endpoints will be characterized using MMRM to estimate change from baseline with treatment group, week, treatment \times week interaction and baseline value as covariates. The model will include all timepoints for subjects in the FAS and will be evaluated for Pain NRS at Week 24 and WOMAC Function and Patient Global Assessment at Weeks 12 and 24.

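### The partial start-date rule in SAP 12.1, reused in 12.3, can score NSAID use already under way as 0 at baseline, and the SAP leaves unresolved whether the protocol's between-arm model for secondary endpoint 4 still applies

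*SAP*

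**What the plan says.** **Endpoint.** Protocol 3.2.2 and SAP 3.2.2 both list as secondary endpoint 4: "Change from baseline in usage of NSAIDs and acetaminophen for target knee OA pain".

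**Protocol analysis.** Protocol 10.4.3 applies an MMRM (treatment, week, their interaction, baseline) to the secondary endpoints. The list it gives ends with "WOMAC Function and Patient Global Assessment at Weeks 12 and 24, as well as change in NSAID/acetaminophen usage". It then asks for unadjusted 95% confidence intervals and P values.

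**SAP analysis.** SAP 9.3.1 opens generically: "Change over time in secondary endpoints will be characterized using MMRM to estimate change from baseline". It then says that the model "will be evaluated for Pain NRS at Week 24 and WOMAC Function and Patient Global Assessment at Weeks 12 and 24". SAP 7.1.2 states that the MMRM "will be used to evaluate Pain NRS, WOMAC, and Patient Global Assessment outcome measures". It gives a Toeplitz covariance for Pain NRS, and then: "For WOMAC and Patient Global Assessment, the model will be estimated assuming an unstructured variance-covariance matrix". SAP 7.1.3 says that ANCOVA "will be used for continuous efficacy outcome measures to test the following hypotheses". For the NSAID score itself, SAP 12.3 plans a statistical description "of Total NSAID Score at baseline will be provided along with the change from baseline at each subsequent visit", plus listings, and Section 12 places medication summaries on the Safety Analysis Set. Section 13 declares one change, the dropped mJSW subgroup.

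**Dates.** SAP 12.3 counts days of use as end minus start plus 1, cut to each 28-day window, and imputes partial dates as in SAP 12.1. SAP 12.1 says its rule assumes maximum exposure. A start known only to the injection year, or only to the injection month, becomes the injection date. An earlier partial start becomes the last day of its month or year. If the imputed start falls after a known end date, it is set to that end date. SAP 7.3.4 says that the pre-dose Day 1 assessment establishes baseline use over the previous 4 weeks.

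**The concern.** The baseline window closes on Day -1, the day before the date to which the rule moves many partial starts. A subject who used a drug all through the four weeks before injection can then appear as a non-user who began on Day 1. That contradicts SAP 7.3.4 and creates an increase in use that never happened. The error enters the endpoint 4 summaries and also Sensitivity 2 in Appendix 3, where change in Total NSAID Score is a covariate.

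Separately, the protocol promises a between-arm estimate for endpoint 4, and it is not clear that the SAP will produce one. Rescue use was freely adjustable (Protocol 7.8), and SAP 4.4.2 says that quantifying it serves to assess its impact on key endpoint data. A clear between-arm comparison therefore matters for reading the pain results.

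**Working it through.** **1. Date rule**

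Inputs from SAP 12.3: baseline window Day -28 to -1; time period 28 days; usual usage 6.5/7, 4.5/7, 2.5/7 or 0.5/7; eqNSAID = 100 × daily dose / reference dose.

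Score per drug = eqNSAID × days in window × usual usage / 28.

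*The plan's own figure first.* A complete start date before the window gives 28 days, the maximum that SAP 12.3 states. At full reference dose the score is 100 × 28 × (6.5/7) / 28 = 92.9. For the lower usage categories it is 64.3, 35.7 and 7.1. At half the reference dose and 6-7 days a week it is 46.4.

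*Injection year only.* The start becomes Day 1 and the end is cut to Day -1, one calendar day earlier. Days = (-1) + 1 = 0, so the score is 0. Weeks 9-12 (Days 57 to 84) still score 92.9, so the change is +92.9 with no change in use. Such a drug can have covered the whole window only if injection was on 29 January or later, since Day -28 is then 1 January.

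*Illustrative cases, full reference dose, 6-7 days a week (92.86/28 = 3.316 per day):*

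| Start recorded | Injection | Start used | Days | Baseline score |
|---|---|---|---|---|
| complete, before window | any | as recorded | 28 | 92.9 |
| 2020 | 17 Aug 2020 | 17 Aug 2020 | 0 | 0 |
| 2020, with end date on Day -1 | 17 Aug 2020 | the end date | 1 | 3.3 |
| 2020-02 | 15 Mar 2020 | 29 Feb 2020 | 15 | 49.7 |
| 2020 | 10 Jan 2021 | 31 Dec 2020 | 10 | 33.2 |
| 2020-01, or 2019 | 15 Mar 2020 | 31 Jan 2020, or 31 Dec 2019 | 28 | 92.9 |

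*Injection month only.* At most the days from the 1st of the month to Day -1 are lost. For injection on the 5th, 15th or 25th that is 4, 14 or 24 days, or 13.3, 46.4 or 79.6 points.

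These are losses per drug. A subject's total falls to 0 only if every drug used at baseline is affected.

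**2. Model for endpoint 4**

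| Place | Treatment of endpoint 4 |
|---|---|
| Protocol 10.4.3 | MMRM, 95% CI, P value; no week named for NSAID use |
| SAP 9.3.1, first sentence; SAP 7.1.3 | generic wording that could include it |
| SAP 9.3.1, list of outcomes | omitted |
| SAP 7.1.2 | omitted; no covariance structure |
| SAP Appendix 3 | never the variable; only a covariate in Sensitivity 2 |
| SAP 12 and 12.3 | descriptive statistics and listings, Safety Analysis Set |
| SAP 13 | not mentioned |

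The generic wording permits a model, but nothing supplies what is needed to run one.

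The score and the endpoint also differ in scope. Total NSAID Score sums all oral use whatever the reason, while the endpoint is limited to target knee OA pain. The Investigator's judgement of whether a change was due to the target knee is only listed.

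For scale, at the re-estimated 225 evaluable subjects per arm a restored contrast would have a 95% half-width of about 1.96 × √(2/225) = 0.185 SD of the change score, before any gain from baseline adjustment. The documents give no SD.

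**3. Sensitivity 2**

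Appendix 3 calls its handling of NSAID use a composite strategy. The outcome is still the unmodified change in pain or function; only a post-randomisation covariate is added. That is not a composite.

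**The case against.** **The rule has a sensible purpose.** Moving a partial start to the injection date captures as much post-injection exposure as possible, which suits the SAP 12.1 summary of drugs begun after injection. That stands for 12.1. It does not carry over to a window that ends before injection, and nothing in 12.3 lets the Day 1 assessment override an imputed date.

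**It may rarely bite.** Source documents must hold start and stop dates (Protocol 11). Exclusion 29 requires a stable regimen for at least 4 weeks before Day 1, so a regular drug begun in the injection month should be uncommon: it could have 28 prior days only if injection fell on the 29th or later. Long-standing users with older partial dates lose nothing. All of this stands, and it narrows the problem mainly to year-only starts in the injection year and to starts shortly before it.

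**Nothing was withdrawn.** A reader might infer that the SAP dropped the endpoint 4 model without declaring it. The documents do not establish that. The first sentence of 9.3.1 may still cover the endpoint, in which case Section 13 had nothing to declare. The missing week is inherited from the protocol, and the confidence-interval sentence is absent from 9.3.1 for every secondary endpoint. What remains is an inconsistency.

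**Indication.** A reader might infer that target-knee attribution exists only in the Investigator's assessment. Protocol 7.5 records an indication for every medication, although it need not name the knee. Protocol 10.4.3 itself refers to usage without a knee qualifier, so the tension begins in the protocol. The cough-and-cold and opioid products in the 12.3 table prove little, since the SAP says that some listed drugs may not have been used.

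**Conclusion.** The date rule is wrong as written for the baseline NSAID score. For a drug used throughout Day -28 to -1 with only the injection year recorded, baseline is 0 and the false change is up to 92.9 at full reference dose, and less in proportion to dose and frequency. Some earlier partial starts leave a truncated baseline.

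The frequency of partial dates is not given. A reader might infer a bias between arms, but none is shown: under double-blind 1:1 allocation the error should be similar in both arms in expectation. It distorts baseline and change scores and adds noise to the Sensitivity 2 covariate.

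On endpoint 4, protocol and SAP are inconsistent, and the SAP as it stands yields no clear between-arm estimate. Endpoint 4 is in neither the protocol's hypotheses (10.2) nor the SAP's six-test sequence (Section 9), so the primary analysis and familywise error control are unaffected. The Sensitivity 2 label is a minor point, and no bias figure is claimed for that analysis.

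**What to change.** 1. **Dates (SAP 12.3).** For NSAID scores, if the drug is recorded in the Day 1 NSAID/acetaminophen assessment, impute a partial start to the earliest date consistent with the recorded part. Otherwise keep the injection-date rule. Report the number of partial dates by arm.
2. **Model (SAP 9.3.1 and 7.1.2).** State that change in Total NSAID Score is analysed by the protocol's MMRM on the Full Analysis Set, outside the alpha sequence, with between-arm difference, 95% CI and nominal P value. Weeks 9-12 and 21-24 with a named covariance structure would be one reasonable choice; the documents do not fix these. If the model is not wanted, declare and justify its removal in Section 13.
3. **Scope.** State that the score covers all oral use whatever the indication. Tabulate by arm and visit the Investigator's assessment of changes due to target knee OA pain.
4. **Label (Appendix 3).** Drop *composite* from Sensitivity 2 and say that it adjusts for a post-randomisation variable.

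The cost is SAP wording and programming on data already collected, with no change to conduct or care.
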